### 3.2.7 Age and age at first diagnosis

The age at Screening Visit will be the determining factor for age cohort assignment (see [Section 2.3](#) and [Section 3.7](#)). For subjects aged 2 years and above, age will be displayed in years, otherwise age will be displayed in months. The age at first diagnosis of epilepsy will be calculated in years and months for all subjects, and will be derived applying all rules for missing data imputation ([Section 4.2](#)). Age at first diagnosis in years will be calculated with the following formula:

$$\begin{aligned} &\text{Age at first diagnosis (years)} \\ &= (\text{Date of first diagnosis of epilepsy} - \text{Date of birth}) / 365.25 \end{aligned}$$

For the calculation of age at first diagnosis in months consider 1 month = (365.25/12) days:

$$\begin{aligned} &\text{Age at first diagnosis (months)} \\ &= (\text{Date of first diagnosis of epilepsy} - \text{Date of birth}) / (365.25/12) \end{aligned}$$

### 3.2.8 Duration of epilepsy

Duration of epilepsy will be calculated in years and months, and will be derived applying all rules for missing data imputation ([Section 4.2](#)).

Duration of epilepsy in years will be calculated with the following formula:

$$\begin{aligned} &\text{Duration of epilepsy (years)} \\ &= (\text{Date of informed consent} - \text{Date of first diagnosis of epilepsy}) \\ &\quad / 365.25 \end{aligned}$$

For the calculation of the duration of epilepsy in months consider 1 month = (365.25/12) days:

---

$$\begin{aligned} \text{Duration of epilepsy (months)} \\ &= (\text{Date of informed consent} - \text{Date of first diagnosis of epilepsy}) \\ & / (365.25/12) \end{aligned}$$

Summary statistics for both durations will be calculated and displayed to 2 decimal places.

### 3.2.9 Amount of Time and number of days of each PCST prior to TEAE onset

The definition of PCST for ECG, Laboratory values and vital signs are described in the relevant sub-sections in [Section 10](#). PCSTs are described in [Appendix 12.2](#). The definition of TEAE is in [Section 10.2](#)

For each TEAE with at least one PCST value at the time of or prior to the adverse event, the number of days and where possible time prior to each TEAE onset relative to each observed PCST will be calculated and displayed. Time prior to each TEAE will only be calculated in days, hours and minutes where the time and date of the TEAE and PCST is available. Imputed AE times will not be used for missing AE times. When the time is missing for the PCST and/or TEAE, but the date of the TEAE is the same or later than the PCST, the TEAE will be assumed to have occurred after the PCST, and only number of days prior to TEAE onset will be calculated.

The formula for time prior to TEAE onset is as follows:

$$\text{Time prior to TEAE onset} = \text{TEAE start day and time} - \text{start day and time of PCST}$$

The formula for number of days prior to TEAE onset is as follows:

$$\text{Number of days prior to TEAE onset} = \text{TEAE start day} - \text{PCST start day}$$

### 3.3 Body mass index (BMI)

BMI will be calculated using weight and height at Screening Visit with the following formula:

$$\text{BMI (kg/m}^2\text{)} = \frac{\text{weight (kg)}}{[\text{height (m)}]^2}$$

### 3.4 Definition of Baseline values

Baseline for laboratory variables (blood chemistry, hematology, and endocrinology), vital signs, body weight, and quantitative electrocardiography (ECG) variables is defined as the latest assessment prior to the first infusion of iv BRV. Both scheduled and unscheduled assessments from the central laboratory are considered.

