4.2.2 Other safety variables

- 12-lead ECG values before, during, and after each iv BRV administration
- BP, pulse rate, RR, and temperature values before, during, and after each iv BRV administration
- Clinical laboratory parameters (hematology, chemistry, and endocrinology) pre and posttreatment
- Urinalysis parameters pre and posttreatment

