12.4.1.2 Other safety variables

Inferential statistical tests are not planned for the other safety variables. In general, for continuous safety variables including ECG measurements including corrected QT interval, and vital sign measurements, the descriptive analyses (n, mean, SD, median, minimum, maximum) for the actual measurement and its change from baseline (defined as most recent pre-iv BRV measurement) will be presented by epochs relative to bolus/infusion. When analyzing categorical data, the number and percentage of subjects in each category will be presented. In addition, shift tables may be used to evaluate the number and percentage of subjects having a different post-iv BRV status when compared with their pre-iv BRV status for each bolus/infusion. Changes in vital signs and ECG parameters will be presented graphically for epochs relative to bolus/infusion.

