### 4.8 Time points by infusion duration

The time points relative to infusion initiation for respective assessments will be as follows: In case value of blood pressure at the “≤1 hr pre-infusion with low PCS BP” time point is low PCS, the additional timepoint will be listed only and not included in summary tables.

- Vital signs time points for 15 min infusion:
  - ≤ 1 hr before initiation of iv BRV
  - 5 min after initiation of iv BRV
  - 10 min after initiation of iv BRV
  - 15 min after initiation of iv BRV
  - 30 min after initiation of iv BRV
  - 60 min after initiation of iv BRV.
  - 2 hr after initiation of iv BRV, only SBP and DBP will be collected.
- Vital Signs time points for Bolus:
  - ≤ 1 hr before initiation of iv BRV
  - ≤ 2 min after initiation of iv BRV

- 
- 5 min after initiation of iv BRV
  - 15 min after initiation of iv BRV
  - 30 min after initiation of iv BRV
  - 60 min after initiation of iv BRV
  - 2 hr after initiation of iv BRV, only SBP and DBP will be collected.
- Electrocardiogram time points for 15 min infusion:
    - $\leq 1$  hr before initiation of iv BRV
    - 5 min after initiation of iv BRV
    - 10 min after initiation of iv BRV
    - 15 min after initiation of iv BRV
    - 30 min after initiation of iv BRV
    - 60 min after initiation of iv BRV
    - 2 hr after initiation of iv BRV
  - Electrocardiogram time points for Bolus:
    - $\leq 1$  hr before initiation of iv BRV
    - $\leq 2$  min after initiation of iv BRV
    - 5 min after initiation of iv BRV
    - 15 min after initiation of iv BRV
    - 30 min after initiation of iv BRV
    - 60 min after initiation of iv BRV
    - 2 hr after initiation of iv BRV
  - Pharmacokinetic time points for 15 min infusion and Bolus:
    - $\leq 1$  hr before initiation of iv BRV
    - 15 min after initiation of iv BRV
    - 3 hr after initiation of iv BRV.

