## **10.5 Vital signs, physical findings, and other observations related to safety**

### **10.5.1 Vital signs and body weight**

Vital signs (systolic blood pressure [SBP], diastolic blood pressure [DBP], respiratory rate [RR], temperature, pulse rate) and body weight will be collected according to the protocol schedule of study assessments.

Observed values of body weight will be summarized for each visit by infusion duration, and by subject group for the SS-iv.

Observed values of SBP, DBP, RR, temperature and pulse rate will be summarized for each time point (as defined in [Section 4.8](#)) within each visit. Change from Baseline for SBP, DBP, RR, temperature, and pulse rate will be summarized for all post-Baseline time points within each visit. Tables will be provided overall and by age cohort, for all subjects and by infusion duration, and by subject group for the SS-iv. Observed values for SBP, DBP, RR, temperature, and pulse rate at each timepoint will be plotted as a line for each subject in line graphs by visit (Visit 1 to 3, then for each visit individually i.e. Visit 4, 5, etc), age cohort and infusion duration. Abnormal values defined by the PCST criteria will be marked using symbols.

Vital signs PCS/PCST definitions are located in [Appendix 12.2.4](#). Vital signs PCST events (i.e. Treatment-emergent vital signs PCS) are defined as events which started on or after the first BRV medication taken during the EP0065 study that meet PCS criteria. Subjects who began the study on BRV treatment (OLB and RxB subjects) will be assumed to have taken BRV treatment on the first day of screening. Therefore, timing of a PCS being treatment emergent (i.e. a PCST) varies by subject group: all PCS are treatment emergent for RxB and OLB subjects; all PCS on or after the IOB Treatment Period are treatment emergent for IOB subjects; all PCS on or after the iv PK Period are treatment emergent for IIB subjects.

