## 10.5.2 Electrocardiograms (ECGs)

Standard 12-lead ECGs (heart rate, RR-interval, PQ/PR interval, QRS duration, QT interval, QTcB interval) will be performed throughout the study, according to the protocol schedule of assessments. The QTcF interval will be calculated using the following formula:

$$QTcF = \frac{QT}{\sqrt[3]{RR}}$$

Observed values of ECG parameters will be summarized for each timepoint within each visit. Change from Baseline for ECG parameters will be summarized for all post-Baseline timepoints within each visit. Tables will be provided overall, and by age cohort for all subjects, and by infusion duration, and subject subgroup for the SS-iv. Values for all ECG parameters at each timepoint will be plotted as a line for each subject in line graphs by visit (Visit 1 to 3, then for each visit individually i.e. Visit 4, 5 etc.), age cohort, and infusion duration. Abnormal values are defined by the PCS/PCST criteria (see [Appendix 12.2.5](#)) and will be displayed using symbols. ECG PCST events (i.e. Treatment-emergent ECG PCS) are defined as events which started on or after the first BRV medication taken during the EP0065 study that meet PCS criteria. In subjects who began the study on BRV treatment (OLB and RxB subjects), they will be assumed to have taken BRV treatment on the first day of screening. Therefore, timing of a PCS being treatment emergent (i.e. a PCST) varies by subject group: all PCS are treatment emergent for RxB and OLB subjects; all PCS on or after the IOB Treatment Period are treatment emergent for IOB subjects; all PCS on or after the iv PK Period are treatment emergent for IIB subjects.

All ECG parameter measurements (scheduled and unscheduled) which are taken after the first BRV medication during the EP0065 study will be assessed to determine if they meet PCST criteria. The number and percentage of subjects that meet the criteria for PCST at each timepoint and visit will be presented for each variable individually overall and by age cohort for all subjects and by infusion duration. A separate summary will be presented by country of enrollment (Hungary and rest of the World) for all subjects and by infusion duration. Percentages will be relative to the number of subjects with a value at each corresponding timepoint or visit.

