The number and percentage of subjects with normal, abnormal not clinically significant, and abnormal clinically significant ECG findings, as assessed by the investigator, will be summarized for all timepoints within visits overall and by age cohort for all subjects and by infusion duration.

Shift tables will display the number and percentage of subjects having the same and different ECG finding (normal/abnormal not clinically significant/abnormal clinically significant) at each post-iv timepoint compared to their pre-iv ECG finding in the same visit, for all subjects and by age cohort, by infusion duration. Therefore, for subjects on bolus the shift from pre-iv BRV to ≤2, 5, 15, 30, 60 minutes and 2 hr after initiation of iv BRV result will be displayed, and for subjects on 15 minutes infusion the shift from pre-iv BRV to 5, 10, 15, 30, 60 minutes and 2 hr after initiation of iv BRV result will be displayed.

A subject data listing will be provided for 12-lead ECG results and will contain a column indicating the PCS and PCST criteria if a subject had abnormal ECG value. A separate listing will be provided, displaying the 12-lead ECG findings including a record of whether each finding was clinically significant or not.

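### From the second infusion on, numeric change in vital signs and ECG is tabulated only against the value before the first infusion, so the spread of the paired within-infusion change is missing from the tables (minor, cheap to add)

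*SAP*

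**What the plan says.** SAP 3.4 gives one Baseline for laboratory values, vital signs, body weight and quantitative ECG: it "is defined as the latest assessment prior to the first infusion of iv BRV". SAP 10.5.1 then states: "Change from Baseline for SBP, DBP, RR, temperature, and pulse rate will be summarized for all post-Baseline time points within each visit". SAP 10.5.2 does the same for ECG: "Change from Baseline for ECG parameters will be summarized for all post-Baseline timepoints within each visit". Both sections also plan tables of observed values at each time point, one plotted line per subject by visit, and full listings.

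Only one planned table compares values within a visit. It is the shift table of the investigator's three-category ECG finding, "compared to their pre-iv ECG finding in the same visit". Vital signs and quantitative ECG have no counterpart. The reference value is available, because SAP 4.8 schedules a reading no more than "1 hr before initiation of iv BRV".

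Protocol 4.2.2 lists as variables "BP, pulse rate, RR, and temperature values before, during, and after each iv BRV administration", with a parallel entry for ECG. Protocol 12.4.1.2 plans "change from baseline (defined as most recent pre-iv BRV measurement) will be presented by epochs relative to bolus/infusion", and its optional shift tables look at subjects' status "when compared with their pre-iv BRV status for each bolus/infusion". SAP 3.10 says that time points replace the protocol's epochs for vital signs and ECG and does not mention the reference value. SAP 13.2 notes that the wording of 3.4 was updated and gives no reason.

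**The concern.** The protocol describes these variables per administration, and PK sampling is planned with the first and one further infusion, so a second infusion is an ordinary part of the design. At infusion 1 the planned change is the within-infusion change. At infusion 2 it is not: a fall after the dose and a pre-dose value that has already drifted are added together.

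The gap is in the spread. With about 6 subjects per cohort and infusion duration, a reader wants to know how far individual subjects moved around that infusion as well as how far they moved on average. Protocol Amendment 1 added a 2-hour blood-pressure reading, as a precaution and not because of any related adverse event, in order to look further at blood-pressure changes. The size of individual moves is part of that question.

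**Working it through.** **Inputs.** Baseline definition: SAP 3.4. Time points: SAP 4.8. Dosing interval of 12 h ±2 h and 1 to 2 usual doses (up to 10): Protocol 5.1. About 12 subjects per cohort, half per infusion duration: Protocol summary and SAP 2.3. The plan states no figure on this point, so there is nothing to reproduce. Treating one visit as one infusion is an inference: Visits 3 to 12 are ten visits, matching the maximum of ten doses.

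**Decomposition.** Write pre_k and post_k for values before and after infusion k. The tabulated change is

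post_k − pre_1 = (post_k − pre_k) + (pre_k − pre_1).

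For k = 1 the second term is zero. For k ≥ 2 it need not be.

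**Age of the Baseline.** Infusion 2 starts 10 to 14 h after infusion 1. Baseline may be taken up to 1 h before infusion 1, so it lies about 10 to 15 h before infusion 2.

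**Share of points.** There are 6 post-initiation points per infusion for ECG and blood pressure, and 5 for pulse rate, respiratory rate and temperature (only blood pressure is taken at 2 h). With two infusions, 6 of 12 and 5 of 10 points respectively use the earlier Baseline.

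**What can be recovered.** Let a = post_2 − pre_1, b = pre_2 − pre_1 and w = a − b. The pre-dose reading of infusion 2 comes after Baseline, so b has its own row. Then

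- mean(w) = mean(a) − mean(b), exact when the same subjects contribute to both rows;
- SD(w)² = SD(a)² + SD(b)² − 2·r·SD(a)·SD(b), where r, the correlation of a and b, is not tabulated.

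The median and range of w likewise depend on the pairing.

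**Example, n = 6 (constructed).** Take b = {−10, −6, −2, 2, 6, 10} in both sets.

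| | Set 1 | Set 2 |
|---|---|---|
| a | −15, −11, −7, −3, 1, 5 | 5, 1, −3, −7, −11, −15 |
| Row b: mean, SD, median, range | 0, 7.48, 0, −10 to 10 | the same |
| Row a: mean, SD, median, range | −5, 7.48, −5, −15 to 5 | the same |
| w | −5 for all | 15, 7, −1, −9, −17, −25 |
| Mean of w | −5 | −5 |
| SD of w | 0 | √(1120/5) = 14.97 |
| Range of w | −5 to −5 | −25 to 15 |

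The row SD is √(280/5) = 7.48. If all six subjects share the same pre_1, the observed-value rows are identical as well, so those tables do not settle it. The median of w is −5 in both sets here, but in general it cannot be had from the row medians.

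**Less extreme cases.** With SD(a) = SD(b) = 10, SD(w) = 10·√(2(1 − r)). For r = 0.3, 0.5, 0.7 and 0.9 this gives 11.8, 10.0, 7.7 and 4.5.

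**Using the observed-value rows too.** Assume SD 10 for pre_1, pre_2 and post_2, and the same correlation ρ of pre_2 and post_2 with pre_1. The tabulated SDs bound the correlation of pre_2 with post_2 only between 2ρ² − 1 and 1. SD(w) can then be anything from 0 to 20·√(1 − ρ²), which is 19.1, 17.3, 14.3 or 8.7 for ρ = 0.3, 0.5, 0.7 or 0.9.

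**The case against.** The strongest reply is that the SAP follows a permissible reading of the protocol. Protocol 12.4.1.2 takes baseline as the latest measurement before iv BRV; read literally, a value taken after infusion 1 no longer qualifies. The per-infusion qualifier is attached only to the optional shift tables, and SAP 10.5.2 supplies such a table for ECG findings. Protocol 4.2.2 asks for values, and observed values are tabulated at every time point. With about six lines per panel, the plots show each subject's course from before to after the dose. The SD of 0 against 15.0 needs correlations of +1 and −1.

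Most of this stands. A reader might infer that the SAP silently departs from the protocol and had to say so in 3.10. The documents do not support that. Reporting relative to each bolus or infusion favours a per-infusion reference, but the definition itself allows both readings, so neither a contradiction nor a duty to list the choice in 3.10 is shown. A reader might also infer that the response to later infusions is lost. It is not: the means can be recovered and the individual data are plotted and listed.

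What remains is that plots of observed values do not tabulate change, and no planned table gives the spread of the paired change.

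**Conclusion.** This is a minor point: a cheap improvement, not an error that threatens any conclusion. From infusion 2 on, the tables give change since before infusion 1, allow the mean within-infusion change to be worked out, and leave its SD, median and range undetermined.

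It does not touch infusion 1, subjects with a single infusion, or the vital-sign PCS limits for subjects under 17 years, none of which uses change from Baseline. The ECG PCST criteria under 17 years for QTc, PR, QRS and heart rate do use it. That is defensible for cumulative effect and needs no change.

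The algebra rests on no assumption beyond the planned tables. All illustrative SDs and correlations are assumptions, because the documents give neither, and how many subjects will have a second infusion is not stated. The variables are secondary and all summaries are descriptive.

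**What to change.** In SAP 3.4, define a second reference for vital signs and quantitative ECG: the scheduled pre-infusion value (within 1 h before the start) of the same infusion. In 10.5.1 and 10.5.2, tabulate the paired change from it with the usual statistics (n, mean and SD, median, minimum and maximum), at least for infusion 2. Index the tables by infusion number, so that they do not rest on the visit count.

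For blood pressure, state which value is the reference when a low PCS pre-dose reading is repeated before dosing. SAP 4.8 keeps the additional time point in the listings only, so simply taking the last value before the infusion would bring repeats into the tables, and those repeats continue until the reading is no longer low. One consistent choice is the scheduled value as reference, with the repeat listed.

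Keep the existing Baseline for cumulative change and the PCST flags, and note both references in the SAP.

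The cost is one derived variable, a few lines of text and some extra tables; the pre-dose values are already collected at every infusion. The drawback is a second set of change tables to label and read, with cells of about 6 subjects or fewer. Limiting the new tables to infusion 2 contains that.

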### 3.5 Protocol deviations

Important protocol deviations are deviations from the protocol which potentially could have a meaningful impact on the primary outcomes for an individual subject. The criteria for identifying important protocol deviations will be defined within the appropriate protocol-specific document. Important protocol deviations will be reviewed as part of the ongoing data cleaning process and data evaluation. Important deviations will be identified and documented prior to database lock to confirm exclusion from the Pharmacokinetic Per-protocol Set (see [Section 3.6.3](#)).

### 3.6 Analysis sets

#### 3.6.1 Safety Set iv (SS-iv)

The Safety Set iv (SS-iv) will include subjects who received at least 1 dose of iv BRV. The SS-iv will be the primary analysis set for the analysis of safety data.

#### 3.6.2 Safety Set (SS)

The Safety Set (SS) will include subjects who received at least 1 dose of BRV (oral or iv). Selected safety summaries will be presented for the SS (see also [Section 3.1](#)).

#### 3.6.3 Pharmacokinetic Per-protocol Set

The Pharmacokinetic Per-protocol Set (PK-PPS) will include all subjects in the SS-iv having provided at least 1 measurable post-dose plasma sample (with recorded sampling time) during the iv PK Period with documented iv BRV infusion times and without important protocol deviations impacting the interpretability of the PK analyses.

### 3.7 Treatment assignment and treatment groups

This is an open-label study with a single treatment arm. The age at Screening Visit will be the determining factor for age cohort assignment. Subjects are summarized in the following age based cohorts (approximately 12 subjects/cohort):

- Cohort 1:  $\geq 12$  to  $< 16$  years
- Cohort 2:  $\geq 6$  years to  $< 12$  years
- Cohort 3:  $\geq 2$  to  $< 6$  years
- Cohort 4:  $\geq 1$  month to  $< 2$  years

### 3.8 Center pooling strategy

The expected number of subjects for most sites is low. In general, it will not be feasible to adjust statistical analysis for site effect and there are no plans to present any study outcomes by site. No pooling strategy is defined for this study.

### 3.9 Coding dictionaries

Medical history and AEs will be coded using the Medical Dictionary for Regulatory Activities (MedDRA) version 18.1. Medications will be coded using the World Health Organization Drug Dictionary (WHODD) version Sep 2017. Medical procedures are not coded.

### **3.10 Changes to protocol-defined analysis**

As iv BRV is defined as the study medication the following parts of the PK-PPS definition were further clarified: "subjects in the SS-iv" instead of "subjects in the SS" and "infusion times" instead of "intake times". Furthermore, the term "without important protocol deviations impacting the interpretability of the PK analyses" was added to the definition of PK-PPS.

Vital sign and ECG summary tables will summarize the subject data for each timepoint but not as stated in the protocol (pre-bolus/infusion period, the bolus/infusion period, the period immediately post-bolus/infusion, and period between each subsequent bolus/infusion). Adverse events tables will not summarize the subject data as specified in the protocol (pre-bolus/infusion period, the bolus/infusion period, the period immediately post-bolus/infusion, and period between each subsequent bolus/infusion). Instead AEs will be summarized by time relative to most recent bolus/infusion start time ( $\leq 5$  minutes,  $> 5$  to  $\leq 15$  minutes,  $> 15$  to  $\leq 60$  minutes,  $> 60$  minutes to  $\leq 12$  hours and  $> 12$  hours).

